Revised total with progression (≥3 steps or PC)	0.068 (97/1429)	0.102 (145/1427)	0.64 (0.49–0.84) P = 0.0010	0.061 (49/806)	0.098 (77/787)	0.59 (0.40–0.86) P = 0.0049	0.099 (64/647)	0.084 (52/616)	1.21 (0.82–1.78) P = 0.33
Baseline step* 1 no DR	0.057 (39/683)	0.071 (49/687)	0.78 (0.50–1.21) P = 0.27	0.062 (25/401)	0.059 (22/375)	1.12 (0.61–2.03) P = 0.72	0.067 (21/314)	0.071 (20/280)	1.00 (0.53–1.92) P = 0.99
Baseline steps 2–4: Ma or mild DR 1 eye, no DR or Ma only in other	0.027 (12/439)	0.084 (38/453)	0.30 (0.15–0.59) P = 0.0002	0.030 (8/264)	0.101 (26/258)	0.27 (0.12–0.63) P = 0.0009	0.046 (8/173)	0.041 (8/197)	1.22 (0.44–3.40) P = 0.71
Baseline steps 5–6: mild/moderate NPDR	0.090 (19/210)	0.119 (21/176)	0.69 (0.35–1.36) P = 0.28	0.068 (6/88)	0.135 (14/104)	0.41 (0.14–1.18) P = 0.09	0.081 (8/99)	0.126 (12/95)	0.61 (0.23–1.62) P = 0.32
Baseline steps 7–9: moderate/moderately severe NPDR	0.198 (16/81)	0.256 (22/86)	0.74 (0.33–1.62) P = 0.45	0.128 (6/47)	0.250 (10/40)	0.44 (0.12–1.62) P = 0.21	0.310 (13/42)	0.237 (9/38)	2.23 (0.64–7.74) P = 0.20
Baseline steps 10–17: severe NPDR or PDR	0.667 (10/15)	0.583 (14/24)	†	0.667 (4/6)	0.5 (5/10)	†	0.706 (12/17)	0.5 (3/6)	†

ACCORD = Action to Control Cardiovascular Risk in Diabetes; DR = diabetic retinopathy; Ma = microaneurysms; NPDR = nonproliferative diabetic retinopathy; PC = photocoagulation; PDR = proliferative diabetic retinopathy.

*See Ref. 7 in the Supplementary Appendix.

†Model did not converge because some cells had too few people.

113

114 *Table taken from Chew EY, Davis MD, Danis RP, et al. The effects of medical management on
115 the progression of DR in persons with type 2 diabetes: the Action to Control Cardiovascular Risk
116 in Diabetes (ACCORD) Eye Study. *Ophthalmology*. 2014;121(12):2443-51.

117

118 In the 8-year follow-up study of ACCORD, 4 years following the cessation of the fenofibrate, the
119 rate of DR progression was 11.8% (N=399) and 10.2% (N=363) in the fenofibrate group and
120 placebo group, respectively, (adjusted OR 1.13, 95% CI 0.71 to 1.79, P=0.60). This suggests that
121 fenofibrate’s protective effect may be dependent on continued dosing.¹⁰

122 A recent systematic review was conducted of randomized trials evaluating either statin, fibrate or
123 combination statin/fibrate among patients with either type 1 or type 2 diabetes with or without
124 NPDR. 1453 studies were initially screened and 8 met the defined eligibility criteria. Of the studies

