 1187 4 weeks. In addition, the participant’s PCP will be contacted by the clinical site to
 1188 determine if there is another cause. If the confirmatory estimated GFR is below
 1189 30mL/min/1.73m² and there is no other attributable cause, the masked study drug will be
 1190 permanently discontinued, regardless of fenofibrate or placebo assignment. The
 1191 participant will remain in follow-up.
- 1192 • If at any time the clinical site becomes aware of an elevated creatinine value from a usual
 1193 care blood draw for which there is no other attributable cause as confirmed by the PCP, the
 1194 participant will be asked to obtain a confirmatory blood draw using the central laboratory.
 1195 Dose-titrations will be made accordingly using the eGFR central laboratory value.
- 1196 • The masked study drug will also be permanently discontinued for the following after
 1197 confirmation from the primary care provider that there is no other attributable cause and a

1198 confirmatory blood draw within 4 weeks (provided there are not substantial symptoms
1199 necessitating immediate discontinuation):

- 1200 ○ ALT > 3x the upper limit of normal (provided there is no other attributable cause)
- 1201 ○ CK > 5x the upper limit of normal (provided there is no other attributable cause,
1202 such as recent high intensity exercise)
- 1203 ○ >50% reduction in HDL from baseline (provided there is no other attributable
1204 cause)
- 1205 ○ Presence of gallstones

1206 • If a fibrate drug is clinically indicated (e.g. for lipid management) and prescribed by
1207 another health care provider, the Study Drug will be discontinued.

1208 • All central laboratory values will be provided to the participant's PCP following each visit.
1209 If the PCP recommends a change to study treatment, the central panel of internists
1210 described below will be consulted first if possible.

1211 **6.1.8 Safety Evaluation**

1212 A central panel of internists will be consulted during the study as needed. A summary of how
1213 often the pre-specified safety protocol was used and how often the panel was consulted will be
1214 reported with the study results.

1215 For all participants, post-visit updates including lab results will be sent to the participant's PCP.
1216 If at any time, the participant's PCP recommends a change to study treatment, the central panel
1217 will be consulted first if possible.

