1372 independent monitoring of adverse events. Cumulative adverse event data are semi-annually
1373 tabulated for review by the DSMC. Following each DSMC data review, a summary will be
1374 provided to institutional review boards. A list of specific adverse events to be reported to the
1375 DSMC expeditiously, if applicable, will be compiled and included as part of the DSMC
1376 Monitoring Plan. The DSMC can request modifications to the study protocol or suspension or
1377 outright stoppage of the study if deemed necessary based on the totality of safety data available.

1378 **8.5 Stopping Criteria**

1379 **8.5.1 Participant Discontinuation of Study Drug**

1380 See section 6.1.7 for per-protocol dose adjustments. Additional rules for discontinuing study drug
1381 use are described below.

- 1382 • The investigator or PCP believes it is unsafe for the participant to continue to receive the drug.
1383 This could be due to the development of a potential side effect of the drug, a new medical
1384 condition or worsening of an existing condition; or participant behavior contrary to the
1385 indications for use of the drug that imposes on the participant's safety. Whenever possible,
1386 the central panel of internists should be consulted prior to discontinuation of the drug.
- 1387 • The participant requests that the treatment be stopped
- 1388 • Participant pregnancy

1389 Even if the study drug is discontinued, the participant will be encouraged to remain in the study
1390 through the final study visit.

1391 **8.5.2 Criteria for Suspending or Stopping Overall Study**

1392 A formal plan for interim data monitoring for both futility and efficacy will be established in
1393 consultation with the Data and Safety Monitoring Committee. In addition, the DSMC may request
1394 suspension of study activities or termination of the study if deemed necessary at any time based
1395 on the totality of safety data available. Review of serious, unexpected, and related AEs by the
1396 Medical Monitor, DSMB, IRB, or the FDA or relevant local regulatory authorities may also result
1397 in suspension of further study agent administration. The FDA and study sponsor(s) retain the
1398 authority to suspend additional enrollment and study agent for the entire study, as applicable. The
1399 study may be discontinued by the Executive Committee (with approval of the DSMC) prior to the
1400 preplanned completion of follow-up for all study participants.

1401

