Chapter 9: Miscellaneous Considerations

1402 9.1 Collection of Medical Conditions and Medications

1403 *Pre-Existing Condition:* Any medical condition that is either present at screening, a chronic
 1404 disease, or a prior condition that could impact the participant’s health during the course of the
 1405 study (e.g., prior myocardial infarction or stroke).

1406 *Medications:* All medication for the treatment of chronic pre-existing conditions, medical
 1407 conditions, and/or adverse events that the participant is currently taking at screening and during
 1408 the course of the study should be recorded. Nutraceuticals and preventative treatment also should
 1409 be recorded.

1410 9.2 Prohibited Medications, Treatments, and Procedures

1411 Alternative treatment for DR or DME in a study eye will not be permitted unless protocol criteria
 1412 in section 5.6 are met or treatment is discussed with and approved by the Protocol Chair or
 1413 Coordinating Center designee.

1414 9.3 Precautionary Medications, Treatments, and Procedures

1415 Participants will be cautioned regarding the use of warfarin (Coumadin), colchicine (Colcrys), and
 1416 immunosuppressants that affect kidney function such as cyclosporine and tacrolimus. If any of
 1417 these are considered, their prescribing health care provider should be made aware that the
 1418 participant may be taking fenofibrate and be instructed to consider adjusting the dose as necessary.

1419 Since bile acid binding resins may bind other drugs given concurrently, patients should take the
 1420 Study Drug at least 1 hour before or 4 to 6 hours after a bile acid binding resin to avoid impeding
 1421 its absorption.

1422 If a fibrate drug is clinically indicated (e.g. for lipid management) and prescribed by another health
 1423 care provider, the Study Drug will be discontinued but follow-up will continue until completion
 1424 of the 4-year (48-month) visit.

1425 Diabetes management is left to the study participant’s medical care provider.

1426 9.4 Prophylactic Medications, Treatments, and Procedures

1427 Not applicable.

1428 9.5 Rescue Medications, Treatments, and Procedures

1429 If criteria are met, alternative treatment for DR or DME in the study eye(s) is considered part of
 1430 usual care.

1431 9.6 Treatment in Non-study Eye

1432 Treatment of DR or DME in a non-study eye is at investigator discretion. Study-provided

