- 1624 • Intention-To-Treat (ITT) Analysis Cohort: all randomized participants irrespective of
1625 treatment received, analyzed according to treatment assignment.
- 1626 • Safety Analysis Cohort: all randomized participants that received treatment (participant
1627 took at least one pill).
- 1628 • Per-Protocol Analysis Cohort: participants who complete the last follow-up visit , achieve
1629 at least 75% compliance with the assigned study drug when required to be taken (prior to
1630 protocol-allowed discontinuation), and do not receive DR or DME treatment without
1631 meeting protocol-specified criteria.

1632 The primary analysis will follow the ITT principle. It will include all randomized participants. The
 1633 data from the ITT cohort will be analyzed according to the group to which the participants were
 1634 assigned through randomization, regardless of treatment received.

1635 A per-protocol analysis will be performed to provide additional information regarding the
 1636 magnitude of the treatment effect. The per-protocol analysis will only be performed if more than
 1637 10% of randomized participants would be excluded by per-protocol criteria.

1638 The ITT analysis is considered the primary analysis. If the results of the per-protocol and ITT
 1639 analyses are inconsistent, the per-protocol analysis will be interpreted with caution. In this
 1640 scenario, exploratory analyses will be performed to evaluate possible factors contributing to the
 1641 differences.

1642 If more than 10% of participants in the placebo group receive fenofibrate, then an additional safety
 1643 analysis will be conducted in which participants will be analyzed according to treatment received
 1644 rather than treatment assigned.

1645 **10.6 Analysis of the Primary Efficacy Outcome**

1646 The primary outcome is a time-to-event outcome over 6 years that will be evaluated using the ITT
 1647 analysis cohort. Marginal Cox proportional hazards regression with robust variance estimation via
 1648 the sandwich estimator will be used to compare treatment groups while controlling for the
 1649 correlation between eyes of the same participant.^{67,68} The treatment group comparison will be
 1650 based on the hazard ratio, which will be presented alongside the corresponding 95% confidence
 1651 interval and P value. Baseline eye-level DR severity will be included as a covariate because eyes

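### The per-protocol cohort in Section 10.5 keeps participants who start a non-study fibrate, so its hazard ratio is modestly diluted toward the null

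*Protocol*

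**What the plan says.** Section 10.5 sets three conditions for the per-protocol cohort: completing the last follow-up visit, adequate pill-taking, and no diabetic retinopathy (DR) or macular edema (DME) treatment outside the protocol's criteria. The pill-taking condition is "at least 75% compliance with the assigned study drug when required to be taken (prior to" (the text runs on) "protocol-allowed discontinuation), and do not receive DR or DME treatment without" meeting those criteria. Use of a non-study fibrate is not mentioned. The stated purpose is to add information on the magnitude of the treatment effect. The analysis is run only if more than 10% of randomized participants would be excluded.

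Section 6.1.7.2 provides: "If a fibrate drug is clinically indicated (e.g. for lipid management) and prescribed by" "another health care provider, the Study Drug will be discontinued". Section 9.3 repeats the rule and adds follow-up: "care provider, the Study Drug will be discontinued but follow-up will continue until completion" of the 48-month visit. Section 8.5.1 lists further reasons for stopping study drug, among them: "The participant requests that the treatment be stopped". It encourages those who stop to remain through the final visit.

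Section 10.5 does foresee crossover, but responds only on the safety side: "If more than 10% of participants in the placebo group receive fenofibrate, then an additional safety" analysis is done by treatment received. Section 1.1.4, on the follow-up of an earlier trial after fenofibrate was stopped, comments that the "protective effect may be dependent on continued dosing".

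**The concern.** A per-protocol analysis asked to inform the size of the effect should not carry exposure that contradicts the group label. Here the compliance check ends at a protocol-allowed discontinuation, and starting an outside fibrate is one. From then on, a placebo participant may take the test drug for years and still count as per-protocol placebo. The same rule keeps a fenofibrate participant who stops early for an allowed reason and spends most of follow-up off drug, although a participant with a 74% pill count is removed.

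Two features add to this. Participants who cross over do not count as exclusions, so crossover alone can never reach the 10% trigger for running the analysis. And Section 10.5 does not define protocol-allowed discontinuation. Because Section 8.5.1 lists participant request, voluntary stoppers may be kept as well.

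At stake is the interpretation of a supportive estimate: it would share the crossover and off-drug dilution of the ITT estimate when it might be expected to be freer of it.

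**Working it through.** **1. Tracing one participant.** Take a placebo participant with good pill counts who is prescribed fenofibrate at month 12 and completes follow-up.
- Last follow-up visit completed: yes.
- At least 75% compliance while study drug was required: yes, judged on months 0 to 12 only.
- No off-criteria DR or DME treatment: yes.

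All three conditions are met and nothing ends the follow-up at month 12, so later person-time is counted as placebo.

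**2. The plan's own figures.** Section 10.3.2 gives 20% placebo events at 4 years, hazard ratio 0.5, 20% loss at 4 years, 90% power and two-sided 5% error, with 676 participants if all are followed for 4 years. A log-rank calculation with exponential event and loss times gives 676.9 participants and about 93 events, so the stated figure reproduces. The fenofibrate rate also reproduces: 1 − 0.8^0.5 = 10.6%.

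**3. Hazards.** Placebo: λ = −ln(0.8)/4 = 0.0558 per year. Fenofibrate: λ/2 = 0.0279 per year.

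**4. Placebo crossover.** Assumptions: 5 years of follow-up without loss; a share q of the placebo group moves to the fenofibrate hazard at time t and stays in the cohort; crossover is unrelated to prognosis. The group hazard is events divided by person-years, and the observed hazard ratio is 0.0279 divided by the mixed placebo hazard.

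Example with t = 1 year and q = 10%, per participant:
- no crossover: 0.2434 events, 4.363 person-years
- crossover: 0.1541 events, 4.552 person-years
- mix: (0.9 × 0.2434 + 0.1 × 0.1541) / (0.9 × 4.363 + 0.1 × 4.552) = 0.2345 / 4.382 = 0.0535
- hazard ratio: 0.0279 / 0.0535 = 0.521

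| Placebo participants crossing over (of 280) | At year 3 | At year 2 | At year 1 |
|---|---|---|---|
| 5% (14) | 0.505 | 0.507 | 0.510 |
| 10% (28) | 0.510 | 0.515 | 0.521 |
| 20% (56) | 0.520 | 0.531 | 0.544 |

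**5. Early stopping on fenofibrate.** Same method, with the hazard returning at once to the placebo level after stopping:

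| Fenofibrate participants stopping | At 3 months | At year 1 | At year 2 |
|---|---|---|---|
| 5% | 0.522 | 0.519 | 0.514 |
| 10% | 0.545 | 0.538 | 0.528 |
| 20% | 0.590 | 0.575 | 0.556 |

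**6. Scale.** With about 93 events, SE(log HR) ≈ 2/√93 = 0.21, so a 95% interval around 0.50 runs from about 0.33 to 0.75.

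**7. With crossover time removed.** Under the assumptions in step 4, the hazard ratio returns to 0.50.

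**The case against.** The best defence is that the wording is deliberate: someone who stops because the protocol says so has followed the protocol, and Section 10.5 never names an on-treatment estimand. That stands in part. A reader might infer that the analysis cannot show the on-treatment effect it was designed for. The documents do not support this: the stated purpose is only magnitude, and the consequence is dilution, not failure.

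Crossover should also be limited. Exclusion 11 in Section 2.2.1 removes people with fibrate use in the prior 12 months or an anticipated need for one. It is tempting to argue that crossover will be heavy because primary care providers receive all central laboratory values. But the visit procedures in Section 5.3.2 list no lipid panel between screening and month 48; the schedule table groups lipids with other serum tests and is ambiguous. It is also tempting to follow a participant who crosses over to year 6, but Section 9.3 commits follow-up only to the 48-month visit.

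The shift from placebo crossover is small against the sampling error in step 6. The analysis is conditional and supportive, and Section 10.5 already calls for caution if it disagrees with ITT. No rule gives weight to agreement between the two.

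Finally, the statistical analysis plan, not shown, may add censoring rules. However, Section 10.5 states the cohort definition outright and does not defer it, so this is a rule as written, not an omitted detail.

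**Conclusion.** The point holds as a modest bias toward the null in a supportive analysis. As written, Section 10.5 keeps placebo participants who start a non-study fibrate in the per-protocol placebo group, and its only crossover provision concerns safety.

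With 5% to 20% of placebo participants crossing over between years 1 and 3, a true hazard ratio of 0.50 reads as about 0.505 to 0.544. Retained early stoppers on fenofibrate can matter more: about 0.545 at 10% and 0.59 at 20% if they stop at 3 months and lose all benefit.

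These shares and times are assumptions; the protocol gives none. They also assume that the outside fibrate has the full study-drug effect. A reader might infer larger shifts, such as 0.526 or 0.556, by treating 10% or 20% as shares of all placebo person-time: 0.50/(1 − 0.5 × 0.10) and 0.50/(1 − 0.5 × 0.20). Those need more or earlier crossover than modelled here, and nothing in the protocol points to it. The ITT primary analysis and its inference are untouched.

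**What to change.** In Section 10.5:
- End a participant's per-protocol follow-up, in either arm, at the last outcome visit before first use of any non-study fibrate.
- State which discontinuations count as protocol-allowed, and in particular whether participant request under Section 8.5.1 does.

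Optionally, report a second version that also ends follow-up at permanent study-drug discontinuation. It needs an explicit caveat: stops under Section 6.1.7.2 depend on eGFR, ALT and CK, and Section 1.4.3 reports drug effects on creatinine, liver tests and creatine phosphokinase, so censoring could differ by arm and be informative.

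Widening the safety trigger from fenofibrate to all fibrates would not address this efficacy point.

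The cost is a wording change and a little programming; Section 9.1 already has medications recorded during the study. The per-protocol analysis would have slightly fewer events, and censoring at first fibrate use may itself be informative. No clinical rule and no part of the primary analysis changes.

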12.1 Ethical Standard

1988

The investigator will ensure that this study is conducted in full conformity with Regulations for the Protection of Human Participants of Research codified in 45 CFR Part 46, 21 CFR Part 50, 21 CFR Part 56, and/or the ICH E6.

1989

1990

1991

12.2 Institutional Review Boards

1992

The protocol, informed consent form(s), recruitment materials, and all participant materials will be submitted to the IRB for review and approval. Approval of both the protocol and the consent form must be obtained before any participant is enrolled. Any amendment to the protocol will require review and approval by the IRB before the changes are implemented to the study. All changes to the consent form will be IRB approved; a determination will be made regarding whether previously consented participants need to be re-consented.

1993

1994

1995

1996

1997

1998

12.3 Informed Consent Process

1999

12.3.1 Consent Procedures and Documentation

2000

Informed consent is a process that is initiated prior to the individual's agreeing to participate in the study and continues throughout the individual's study participation. Extensive discussion of risks and possible benefits of participation will be provided to the participants and their families. Consent forms will be IRB-approved, and the participant will be asked to read and review the document. The investigator will explain the research study to the participant and answer any questions that may arise. All participants will receive a verbal explanation in terms suited to their comprehension of the purposes, procedures, and potential risks of the study and of their rights as research participants. Participants will have the opportunity to carefully review the written consent form and ask questions prior to signing.

2001

2002

2003

2004

2005

2006

2007

2008

2009

The participants should have the opportunity to discuss the study with their family members and their personal physicians(s) or think about it prior to agreeing to participate. The participant will sign the informed consent document prior to any procedures being done specifically for the study. The participants may withdraw consent at any time throughout the course of the trial. A copy of the informed consent document will be given to the participants for their records. The rights and welfare of the participants will be protected by emphasizing to them that the quality of their medical care will not be adversely affected if they decline to participate in this study.

2010

2011

2012

2013

2014

2015

2016

For participants who enrolled in the trial prior to protocol v6.0, which extended follow-up from 4 to up to 6 years, an informed consent addendum will be presented to ask if the participant wishes to continue in the trial beyond 4 years. A verbal explanation of the procedures and expected timeline for the individual participant will be presented along with the written informed consent addendum since total expected duration of follow-up will depend on when the participant was enrolled in the trial.

2017

2018

2019

2020

2021

2022 **12.3.2 Participant and Data Confidentiality**

2023 Participant confidentiality is strictly held in trust by the participating investigators, their staff, and
 2024 JCHR and their agents. This confidentiality is extended to cover testing of biological samples and
 2025 genetic tests in addition to the clinical information relating to participants. Therefore, the study
 2026 protocol, documentation, data, and all other information generated will be held in strict confidence.
 2027 No information concerning the study, or the data will be released to any unauthorized third party
 2028 without prior written approval of JCHR.

2029 The study monitor, other authorized representatives of JCHR, representatives of the IRB,
 2030 regulatory agencies or company supplying study product may inspect all documents and records
 2031 required to be maintained by the investigator, including but not limited to, medical records (office,
 2032 clinic, or hospital) and pharmacy records for the participants in this study. The clinical study site
 2033 will permit access to such records.

2034 The study participant’s contact information will be securely stored at each clinical site for internal
 2035 use during the study. At the end of the study, all records will continue to be kept in a secure
 2036 location for as long a period as dictated by the reviewing IRB, institutional policies, or JCHR
 2037 requirements. Separately from any research data, JCHR, will be provided with participant contact
 2038 information to aid in study retention efforts. Name and mailing address will be provided to the
 2039 central pharmacy for study drug distribution. Study participant’s contact information will be
 2040 securely stored and will be destroyed at the end of the study at both the JCHR and central
 2041 pharmacy.

2042 Study participant research data, which is for purposes of statistical analysis and scientific reporting,
 2043 will be transmitted to and stored at JCHR. This will be stored separately from the participant’s
 2044 contact or identifying information. For research purposes, individual participants and their
 2045 research data will be identified by a unique study identification number. The study data entry and
 2046 study management systems used by clinical sites and by JCHR research staff will be secured and
 2047 password protected. At the end of the study, all study databases will be de-identified and archived
 2048 at the JCHR.

2049 To further protect the privacy of study participants, a Certificate of Confidentiality will be
 2050 available from the NIH. This certificate protects identifiable research information from forced
 2051 disclosure. It allows the investigator and others who have access to research records to refuse to
 2052 disclose identifying information on research participation in any civil, criminal, administrative,
 2053 legislative, or other proceeding, whether at the federal, state, or local level. By protecting
 2054 researchers and institutions from being compelled to disclose information that would identify
 2055 research participants, Certificates of Confidentiality help achieve the research objectives and
 2056 promote participation in studies by helping assure confidentiality and privacy to participants.

2057 **12.3.3 Future Use of Stored Data**

2058 After the study is completed, the de-identified, archived data will be made publicly available for
 2059 use by other researchers including those outside of the study. In addition, OCT scans, fundus
 2060 photographs, and fluorescein angiograms will be made publicly available. These images of the
 2061 retina are considered identifiable information but are only identifiable if they can be matched to a
 2062 database that already includes retinal images for identification purposes (directly identifiable

2063 information will be removed). Permission to make data and retinal images publicly available will
2064 be included in the informed consent form.

2065 In addition, serum samples will be stored indefinitely and the de-identified samples made available
2066 to collaborators as described above. Data generated from optional serum samples will be analyzed
2067 in the context of this study but may also be explored in aggregate with data from other studies.
2068 The availability of a larger dataset will assist in identification and characterization of important
2069 biomarkers and pathways to support future biological discoveries.

2070 For participants who consent, the optional RNA sample collected as part of this study will be
2071 provided to the Roche Group and they will store, maintain and use those samples for future
2072 research. They may also provide samples to other researchers and industry collaborators. The
2073 samples and information could be used for publications, other research, to help design future
2074 studies, and to help discover new ways for personalized treatments.

2075

2076

Chapter 13: References

- 2077 1. International Diabetes Federation: Facts and figures. 2014;
2078 <http://www.idf.org/worlddiabetesday/toolkit/gp/facts-figures> Accessed 26 September
2079 2016.
- 2080 2. Varma R, Bressler NM, Doan QV, et al. Prevalence of and risk factors for diabetic macular
